12.0 Withdrawal of Subjects

- 12.1** If women are incarcerated during 6 months of study participation, and if participants fail to attend scheduled visits during 6 months of study participation for more than 3 months, participants may

be subject to study withdrawal without their consent. Participants deemed eligible for study withdrawal by the PI will be informed of the decision by phone or mail.

Participants who were terminated on their study participation will not be followed up for periodic assessments or monthly home visitations. However, if participants need assistance in breastfeeding and other psychosocial issues, research staff provides referrals to appropriate community and hospital services.

13.0 Potential Benefits to Participants:

- 13.1** We believe that the aforementioned risks are reasonable in relation to the anticipated benefits to the mother and infant from continued BF. Participants receive direct benefits from participating in the study to increase access to existing breastfeeding support available in the community. Participants in the SC+BFI group may also experience increased motivation and confidence to continue breastfeeding for 6 months and beyond. In addition, the proposed project has the potential to provide important new scientific information regarding developing effective strategies for maintaining BF during 12 months. We believe the combined direct therapeutic benefits to subjects and new scientific information to be gained in the proposed studies outweigh any risks involved.

14.0 Financial Compensation:

- 14.1** There are three kinds of financial compensations involved in the study.
- 1) Contingent incentives on breastfeeding for participants in SC+BFI: This will be paid immediately and remotely on a Master Card as soon as breastfeeding is confirmed. The amount in the first month home visitation will be \$20, increasing by \$10 every month, for a total potential earning of \$270. Participants in this group will also be eligible to receive \$50 per selection of full breastfeeding food package at WIC at baseline, 3 months, and 6 months postpartum. Thus, a potential total earning in this group is \$420.
 - 2) Incentives on home visitations for participants in SC: This will be paid at the end of 6 months based on the number of completed home visitations. The amount per home visit will be \$40 for a total potential earning of \$240. This will be paid in form of retail gift cards.
 - 3) Assessment compensations for all participants: This will be paid after each completed assessment in form of retail gift cards. After phone assessments one week prior to home visitation appointments, \$20 gift cards will be delivered at the next home visitation appointment. At baseline, 9, and 12-month, \$40 will be paid in person at their home after in-person assessments.
- 14.2** Contingent incentives on breastfeeding in SC+BFI will be provided immediately upon each monthly home visitation. Incentives on home visitations in SC will be prorated at the end of 6 months based on the number of completed home visitations. Payments for completing assessments will be provided after each assessment in person.

Participants in SC+BFI will receive dollar amount incentives on a pre-paid credit card for breastfeeding. This type of system functions just like a Master Card and allows remote reloading. This system has been feasibly and effectively used by

clinical populations. Un-blinded Project Coordinator will credit a dollar amount remotely on a Master Card for each participant.

Payments for home visitations for participants in SC and for assessments for all participants will be provided in form of retail gift cards in person.

- 14.3 Payments for assessments for all participants and contingent incentives for breastfeeding in SC+BFI will be provided immediately after each completion. If participants in SC withdraw before study completion, incentives will be paid based on the number of completed home visitations prior to withdrawal.
- 14.4 Since interventions and assessments occur in their homes or over the phone, we do not anticipate any costs incurring on the participants' side. Depending on the participants' calling plan of their phones and whether they choose to use their phone minutes or Wifi connections, phone minutes may be consumed during phone assessments at 1, 3, and 6-month postpartum.

15.0 Provisions to Protect the Privacy Interests of Participants:

- 15.1 Following screening and consenting during the hospital stay, all in-person home visitations and assessments will occur in participants' home setting where participants can ensure privacy during data collection according to their standard.
- 15.2 All data collection after screening and consenting during the hospital stay, except for three phone-based assessments, will occur in participants' home setting, where adequate privacy will be provided according to the participants' standard.
- 15.3 1, 3, and 6-month assessments will occur over the phone one week prior to the next monthly home visitation. Phone appointments will be made in advance so that participants can ensure privacy during the assessment calls. Research staff will make calls in a private research room.
- 15.4 Only investigators, project coordinator, and research assistants are permitted to access identifiable information about the participants.

16.0 Confidentiality and Data Management:

- 16.1 Written consents, surveys conducted by research assistants, progress notes, notes of breastfeeding observation, height of infants, weights of participants and their infants, hip and waist measures of participants, saliva samples of participants, and anal swabs of infants, will be collected, analyzed, and stored.
Written consent will be stored in a locked filing cabinet at Temple University College of Public Health, separate from de-identified information. Other surveys, progress notes, notes of observation are stored in a password-protected electronic database (RTI-licensed RedCap). There may be paper and pencil version of these information when electronic means are not available. Paper-and-pencil versions will be stored in a locked filing cabinet at Temple University College of Public Health, separate from identifiable information. Biological samples will be stored in a freezer below -80 degrees at Temple University College of Public Health. Written data and biological samples will be transported in a locked baggage.
- 16.2 Data and biological specimens will be de-identified and stored for 5 years.

Only investigators, project coordinator, and research assistants are permitted to access the stored data and specimens.

Investigators, project coordinator, and research assistants are permitted to access the stored data and specimens.

- 16.3** All research staff will be trained on how to transport and store physical data and biological samples, as well as electronic data. They will be trained on how to use an online password-protected data management system (RedCap). Identifiable information on physical materials will be stored in a locked filing cabinet at Temple University College of Public Health or in a password-protected electronic file on a secure online database, separate from de-identified information. If electronic files are shared by email, emails will be encrypted. All biological samples will be de-identified.
- 16.4** We use encrypted emails to transmit de-identified datasets in a password-protected electronic file. We may also use OneDrive or an institution-specific secure server for storing non-data support documents such as meeting minutes, roasters, agendas etc, according to RTI policies and procedures.
- 16.5** Data use agreements will be developed among Temple University, Christiana Care, and RTI.

17.0 Data Monitoring Plan to Ensure the Safety of Participants:

- 17.1** A data safety monitoring (DSM) plan will be developed for this project with six experts in biostatistics/epidemiology, biobehavioral ethics, and obstetric and pediatric clinical care ([name] from Public Health Management Cooperation, [name] at University of Washington (Chair), and [name] at University of Delaware), and the data safety monitoring board (DSMB) will review the plan and determine whether the project requires on-going review by the DSMB or if monitoring by the PI is sufficient. This decision will be completed prior to the commencement of data collection.

The PI will be primarily responsible for monitoring the safety and efficacy of this study, executing the Data and Safety Monitoring Plan (DSMP), complying with any reporting requirements, and consulting with the DSMB when the study needs to be terminated for observed early clinical significances among the first 20 participants.

If the DSMB decides that the study will be monitored by the DSMB on an ongoing basis (in addition to the required IRB monitoring), the PI will provide a summary of the DSM reports to NICHD on an annual basis (along with IRB reports). The DSM report will include the participants' socio-demographic characteristics, expected versus actual recruitment rates, retention rates, quality assurance, or regulatory issues that occurred during the past year, a summary of Adverse Events (AEs) and Serious Adverse Events (SAEs) and any actions or changes with respect to the protocol. The DSM report will also include, when available, the results of any interim outcome analyses. In addition to the annual DSM report, the PI will be responsible for informing NICHD of any IRB actions within two weeks of their occurrence as well as any substantial changes or amendments to the study protocol prior to their implementation.

18.0 Data Sharing, Future Use, and Storage:

- 18.1 Individual-level study data may be shared with collaborators at Temple University, Christiana Care, and RTI. De-identified biological samples will be shipped to an external laboratory for analyses.
- 18.2 Identifiable information will be stored separately from de-identified information. It is possible that collaborators and research staff link identifiable information with de-identified information. Data use agreement will be developed among the three institutions. Electronic files will be shared by encrypted emails. Identifiable information on physical materials will be transported in a locked baggage. De-identified biological samples will be shipped to a laboratory in a secured shipment method.
- 18.3 De-identified information, including surveys conducted by research assistants, progress notes, notes of breastfeeding observation, height of infants, weights of participants and their infants, hip and waist measures of participants, saliva samples of participants, and anal swabs of infants, will be shared.
- 18.4 Data and biological specimens will be banked for 5 years after study completion at Temple University College of Public Health. Only collaborators and research staff of this project have direct access to the specimens and identifiable information. Biospecimens or/and de-identified data may be banked and shared with collaborators outside of this project in the future, in which case data use agreement will be developed with collaborators outside of this project.
- 18.5 Data will be stored electronically on an online password-protected data management system (RedCap). This will be under RTI license, and available for use for 5 years after study completion.
- 18.6 Data use agreement will be developed for those interested in accessing data or results of analyses of specimens. Only de-identified data from surveys, observation notes, measurements of participants and the infants, and results of biospecimen analyses will be provided upon approvals on data release.

22.0 Qualifications to Conduct Research, Resources Available, and Quality Control:

- 22.1 All project staff members having contact with participants undergo training in human subjects protection (provided by CITI training website) and training on HIPAA. Verification of successful completion of these trainings is kept in a designated project binder. All staff complete an extensive training checklist that includes: background reading, viewing PowerPoint training modules, listening to recorded interviews, role playing mock interviews, and observing on home visits. Staff are given feedback on role plays and record all their interviews with study participants. Ongoing quality control checks are conducted on a portion of recordings and feedback is provided to the interviewer. In addition, the research staff will be specifically trained in informed consent procedures to ensure that they are well-versed in the study protocol and able to answer participant questions and that their presentation of the study and informed consent procedures accurately communicates study risks, voluntary participation, and the right to withdraw from the study at any time. They must role-play the informed consent process under observation of the PI and meet criterion before completing the informed consent process with study participants. Documentation of satisfactory completion of informed consent training is also kept in the designated study binder. In addition to the human subjects protection training

mentioned above, all research staff are required to undergo training in confidentiality procedures that review data handling procedures and responding to questions about participants posed by individuals outside of the immediate project staff and by project staff members who do not need the information requested. Certification of successful completion of this training is kept in the designated project binder.

PI holds weekly meetings with [name] and research staff at Temple University College of Public Health for project formation and supervision of implementation/problem solving. PI has experiences of conducting clinical trials since postdoctoral fellowship and was the PI of NICHD-funded R03 on increasing breastfeeding with health incentives and currently managing a clinical trial on prenatal smoking cessation at Christiana Care. [name] is a senior investigator with experiences of running R01s as the PI.

PI also holds biweekly meetings with [name], [name], and [name] with research staff separately at Temple University Hospital and Christiana Care. [name] is an internationally licensed lactation consultant and trained obstetrics and gynecologist and will provide clinical oversight for participants recruitment and follow-up. [name] is the department chair of Obstetrics and Gynecology. [name] is a senior biostatistician at Christiana Care. [name] will assist in data analysis and randomization process.

22.2 There will be no anticipated resources that participants might need as a result of participation in the research.

22.3 All project staff members having contact with participants undergo training in human subjects protection (provided by CITI training website) and training on HIPAA. Any updates on the protocol, research procedures, and staff duties and functions will be updated on either weekly or biweekly meetings among [name], clinical investigators, research investigators, and research staff. Study staff are trained by [name] and project coordinator in how to collect, transport, and enter data into a password-protected online data management system (RedCap), into a locked filing cabinet at Temple University for hardcopy materials, and into a freezer for biological samples at Temple University. Initial training will be done with step-by-step instructions by either [name] or the project coordinator first. Random unannounced checks will be provided at least twice monthly for data entry and management.

For breastfeeding observation and home visitation, study staff are trained by shadowing Temple University Hospital staff or Christiana Care staff who already provide breastfeeding support and/or home visitations. Shadowing will be done at least twice or across two incidents. [name] will also assist in initial stages during the study period for breastfeeding observation and home visitations until [name] observation match with study staff' observation consistently across at least two participants.

For collecting biological samples, study staff are trained by Temple University training courses or equivalent training courses at an education institution or Christiana Care on collecting and handling biological specimens. [name] will train study staff for particular methods according to noninvasive means defined by OHRP Category 3 and WHO for swab and saliva sample collection and have study staff collect samples across at least two participants under [name] supervision.

For assessments, the project coordinator will train study staff in how to conduct assessment interview questions both in person and by phone. The project coordinator will specifically focus on how to capture the attention of a participant while reading each question verbatim on the phone and in person.

22.4 Any updates on the protocol, research procedures, and staff duties and functions will be updated on either weekly or biweekly meetings with [name], clinical investigators, research investigators, and research staff. Communicating in team meetings at each site will be essential prior to implementing any modifications of the protocol. [name] and the project coordinator will maintain all approved documents, and signed contracts/data sharing agreements both at a Temple University shared folder (OneDrive or TempleOwl secure server) and RTI password-protected computer.

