9.2 Inclusion and Exclusion Criteria

To be eligible for the study, mothers must: (1) initiate BF; (2) be WIC-enrolled or eligible to enroll in WIC services; (3) reside and plan to stay in the study county for 12 months postpartum; (4) consent voluntarily; (5) understand 5th grade level of English; and (6) be 18 years or older. We will exclude mothers whose babies are medically contraindicated against BF, who are hospitalized for severe postpartum medical issues, who have ongoing illicit drug use issues, who had a psychiatric hospitalization within the last three months, who currently have suicidal thoughts or attempts. For women who are incarcerated during 6 months of study participation as well as participants who fail to attend scheduled visits during 6 months of study participation for more than 3 months, their study participation will be terminated.

We include infants of the participants, but infants are not subject to inclusion criteria. Written permission for a minor by a parent or legal guardian will be required for infant participants.

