Missing values. We will use an intent-to-treat analysis treating missing values for breastfeeding (BF) status as non-BF status. In addition, the mixed effect models will provide valid estimates of efficacy if the proportion of missing values is less than 10%.¹

Interim analyses. Three interim analyses will be conducted to formally monitor the accumulating data in the study, at 2 months, 4 months, and 6 months, with expected increase of BF rate by 25% as a significant increase at 6-month postpartum. With the overall proposed recruitment number of 168 participants, the α -levels are 0.012, 0.016, and 0.022 for 2-month, 4-month, and 6-month postpartum, based on the standardized Z-values for the two groups from the O'Brien-Fleming function with cumulative $\alpha=0.05$ with power of 85%. If we do not see significant increases (at pre-required α -level) either at 2 or 4 months, we will increase the number of participants to recruit to sustain the power.

Logistic regression will be used to compare groups on the primary binary outcomes of point-prevalence of BF status at 1-, 3-, 6-, and 12-month postpartum; survival analyses will also be used to assess continuation. The models will include terms for study group, time, and the group by time interaction. Although propensity score-matched randomization will minimize the need for covariate adjustment, theoretically important covariates and differences will be considered for inclusion in adjusted analyses to improve their precision. Since the 12-month postpartum BF rate is an exploratory outcome, we will use a conservative significance level of .001 versus .05 for BF rates at other time points to decrease the possibility of having a false-positive statistical outcome. The Cochran-Armitage Trend Test will also be used to examine the trend of BF from 1-month through 6-month postpartum and from 1-month through 12-month postpartum. These analyses will also be used to examine the impact of *SC+BF1* on exclusive BF rates at each time point.

References

1. Bennett DA. How can I deal with missing data in my study? *Australian and New Zealand journal of public health*. 2001;25(5):464-469.

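### Section 12.1 stops all data collection for mothers terminated for missed visits, so the protocol itself creates avoidable missing outcomes at 6, 9 and 12 months

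*Combined protocol and SAP*

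**What the plan says.** - **Trigger.** Section 9.2 treats missed visits as a ground for ending participation: "participants who fail to attend scheduled visits during 6 months of study participation for more than 3 months, their study participation will be terminated". Section 12.1 gives the same trigger, but says that such participants may "be subject to study withdrawal without their consent", with the PI deciding. Incarceration during the first 6 months is the other ground in both sections.
- **After termination.** Under Section 12.1, terminated mothers "will not be followed up for periodic assessments or monthly home visitations". What remains is referral to community or hospital services.
- **Primary outcome.** Section 9.5 defines 6-month breastfeeding (BF) by direct observation of feeding, or of pumping and feeding the pumped milk.
- **Missing data.** The SAP (Statistical Design and Power, Missing values) specifies an "intent-to-treat analysis treating missing values for breastfeeding (BF) status as non-BF status". Its next sentence says that mixed models give valid estimates when less than 10% of values are missing, and names no outcome. No analysis model or missing-data rule is stated for infant weight or emergency room visits.
- **Infant outcomes.** Aim 2 covers 12 months of follow-up. The stated infant hypotheses (Section 4.2) are at 3 months.
- **Pay for attending.** Section 10.2 pays Standard Care (SC) mothers $40 per completed home visit, as a lump sum after month 6. Under Section 10.3, a mother in the incentive arm (SC+BFI) gets no incentive for a visit that she misses or at which BF is not shown.

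**The concern.** Ending the monthly visits and ending data collection are different decisions, and Section 12.1 takes both at once. These mothers are randomised and have not withdrawn consent. Some might still be seen at the 6-month visit or at the 9- and 12-month assessments, but the protocol tells staff not to try. The SAP then fills the 6-month gap with an assumption about feeding status, and the later infant data that Aim 2 needs are never collected.

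The loss need not be neutral between arms. An SC+BFI mother who has stopped BF earns no incentive by attending, while an SC mother is paid for the visit whatever her feeding status, though only later. Who gets terminated may therefore depend on arm and on BF status. The conflict between Sections 9.2 and 12.1 adds discretion over which mothers lose their outcome data.

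**Working it through.** **1. What termination removes.** The trigger is more than 3 months of missed visits within the first 6.
- *3-month infant data.* If these are missing, the missed visits caused it. Termination comes later.
- *6-month BF observation.* Only an absence that starts by about month 3 can lead to termination before the 6-month visit. The rule's own effect is limited to those mothers who would otherwise have been seen again at month 6.
- *9- and 12-month BF data, and infant data after termination.* These are lost for every terminated mother. Infant values from before termination remain.

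**2. Shift in the 6-month difference.** Let t be the share of an arm that is terminated before month 6 and b the share of those mothers still breastfeeding. Coding them as not breastfeeding lowers that arm's rate by t × b. The difference (SC+BFI minus SC) therefore moves by

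shift = t_SC × b_SC − t_BFI × b_BFI.

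The documents give no termination rate, so every input here is an assumption: 5% in one arm, 10% in the other, and b from 20% to 45% in both arms. The low end of b matches the 6-month rate quoted for Medicaid-eligible mothers in Delaware (20%). The high end is close to the Pennsylvania rate (45.7%). Both rates are in Section 5.1.

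| Terminated SC / SC+BFI | b = 20% | b = 45% |
|---|---|---|
| 10% / 5% | 0.020 − 0.010 = +1.0 point | 0.045 − 0.0225 = +2.3 points |
| 5% / 10% | 0.010 − 0.020 = −1.0 point | 0.0225 − 0.045 = −2.3 points |
| any, b = 0 | 0 | 0 |

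A plus sign overstates the incentive effect and a minus sign understates it. The table treats every terminated mother who is still breastfeeding as one who would have been observed, so for given t and b it is an upper limit on what the rule itself does.

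**3. Equal termination and power.** The plan's own figure is 168 mothers (84 per arm) for a 25% increase at 85% power, with a 6-month alpha of 0.022. No control rate or sidedness is given, so 168 cannot be checked uniquely. Reading 25% as 25 points and alpha as two-sided, the pooled two-proportion formula gives 152, 174 and 170 for control rates of 20%, 34.4% (Delaware) and 45.7%. With a continuity correction, 20% against 45% gives exactly 168.

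Now suppose that 10% of each arm is terminated and that these mothers breastfeed at their arm's rate. Each rate is multiplied by 0.9, so the difference becomes 25 × 0.9 = 22.5 points. Power is

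Φ[(d − z × SE0) / SE1],

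with z = 2.290 for two-sided 0.022, SE0 the pooled and SE1 the unpooled standard error at 84 per arm. For a 20% control rate the observed rates are 18.0% and 40.5%, so SE0 = 0.0702 and SE1 = 0.0680. Then (0.225 − 2.290 × 0.0702) / 0.0680 = 0.94, and power is 82.8%.

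| Control rate | Power, none terminated | Power, 10% terminated per arm |
|---|---|---|
| 20% | 88.7% | 82.8% |
| 34.4% | 83.8% | 75.2% |
| 45.7% | 84.8% | 74.1% |

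The 10% is again an assumption.

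**The case against.** Four arguments on the other side have force.

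- **The numbers may be small.** Pilot follow-up was 97% at 6 months (Section 10.4). Section 10.3 provides a one-week make-up window, three phone attempts and then an unannounced home visit. Diapers and wipes at visits, and gift cards for assessments in both arms, soften the attendance gap. This stands: the assumed 5% and 10% exceed the pilot's total loss of about 3%.
- **The direction is open.** A reader might infer that the rule inflates the SC+BFI effect, or flatters its infant results. The documents do not support that. If stopping BF removes the reason to attend in SC+BFI, more terminations would fall in that arm, mostly among mothers for whom the non-BF code is correct. If breastfeeding mothers are terminated more often in SC+BFI, the effect is understated.
- **Intent-to-treat is not contradicted.** A reader might also say that Section 12.1 breaks the SAP's intent-to-treat analysis. It does not: the missing-values rule keeps every randomised mother in the BF analysis. The point is that an assumption replaces data that could have been sought.
- **A phone report is not the endpoint.** Section 9.5 requires observed BF, and infant weight cannot be taken by phone. This stands, and it limits what phone follow-up can restore.

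None of these gives a reason to stop trying. The retention steps act before termination, and nothing in the documents provides for follow-up, a substitute source or a sensitivity analysis after it.

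**Conclusion.** The point holds as an avoidable loss of data, not as a demonstrated bias. Section 12.1 ends collection in consenting randomised mothers. For those terminated before month 6, the primary outcome is then imputed as non-BF, and their 9- and 12-month BF data and later infant data are not collected. The 3-month infant comparison is largely unaffected by termination. It would also be too strong to call the infant outcomes simply lost, since earlier values remain and could be analysed.

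Under the stated assumptions the 6-month difference moves by at most 1.0 to 2.3 points in either direction, and by nothing if all terminated mothers have stopped BF. Equal termination of 10% turns a 25-point difference into 22.5 if terminated mothers breastfeed at their arm's rate. The true size depends on a termination rate that the documents do not give. This is a change that should be made because it is cheap. It is not a flaw that invalidates the trial.

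**What to change.** 1. In Section 12.1, separate ending the monthly support visits from ending data collection. For mothers terminated for missed visits, unless consent is withdrawn, still attempt the 6-month home observation and the 9- and 12-month in-person assessments, so that observed BF and infant weight are obtained where possible.
2. Where only phone contact is possible, collect reported feeding status and the maternal/infant health survey. Section 10.7 does not list that survey, or the infant-feeding log, in the 6-month phone battery, so add feeding status and the survey to that call. Use phone-reported BF in a sensitivity analysis only, never as the observed primary endpoint.
3. Reconcile Section 9.2 ("their study participation will be terminated") with the discretionary wording of Section 12.1.
4. Report terminations by arm and by reason.

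The cost is protocol wording, a few more contact attempts by existing staff, and assessment payments already in Section 14.1 ($20 for the 6-month call, $40 each at 9 and 12 months). Some mothers will remain unreachable, and for them the existing rule still applies.
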